#### 8.6. Procedure(s) to account for missing or spurious data

The extent of missing data will be examined and the reason for missingness ascertained. Multiple imputation (MI) may be used to impute missing values if necessary and where assumptions for missing at random data are met.

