#### 3.5. Table of Endpoints and outcomes:

**Timepoints:** Face to face assessments at baseline, mid-chemotherapy, end of chemotherapy (timing depends on chemotherapy schedule), with all detailed measures. Note: Blood sampling MRI and use of physical activity monitor are optional (participant preference); MRI will be

offered to 100 eligible participants sequentially. Participants will complete a reduced questionnaire set prior to every cycle of chemotherapy. This can be completed remotely (paper/email/telephone/online) according to participant preference. Pain measures are only completed if pain is present.

Objectives	Outcome Measures	Timepoints measured
Primary		
Development (or persistence) of painless or painful CIPN	EORTC-CIPN20     Change in chemotherapy/dose reduction due to neurotoxicity.	Baseline, mid and end of chemotherapy 3, 6, 9 and 12 months after completion of chemotherapy.
	Pain location: List of body sites / Body map.	Baseline, mid and end of chemotherapy 3, 6, 9 and 12 months after completion of chemotherapy.
	Total Neuropathy Score clinical (TNSc)	Baseline, mid and end of chemotherapy.
Pain severity	
 
Chronic Pain Grade
 
Brief Pain Inventory (BPI) Numeric Rating Scale (average in last 24 hours)
 
	Baseline mid and end of chemotherapy at 3, 6, 9 and 12 months after completion of chemotherapy.
Secondary		
Lifestyle	
 
Eastern Cooperative Oncology Group (ECOG) Performance Status Scale
 
Any changes to planned oncological treatment
 
	
 
Baseline, mid and end of chemotherapy
 
Baseline, mid and end of chemotherapy
 

	Past medical History/ co-morbidities     Family History     Details of cancer type and stage     Oncological treatment including         planned chemo protocol (and any changes to this with reasons)     Duration of CIPN     Smoking questionnaire     Alcohol questionnaire     Illicit drugs	• Baseline
	Concomitant medication	Baseline, mid and end of chemotherapy at 3, 6, 9 and 12 months after

	
 
Physical function: Saltin-Grimby Physical Activity Level Scale
 
Step count (ActivPAL™ accelerometer)
 
Patterns of daily living (time spent sitting,
 
	
 
completion of chemotherapy.
 
Baseline, mid and end of chemotherapy at 3, 6, 9 and 12 months after completion of chemotherapy.
 
Baseline, mid and end of chemotherapy
 

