#### 8. STATISTICS AND DATA ANALYSIS

## 8.1. Sample size calculation

The sample size of n=200 will provide a robust, high- quality dataset of deeply phenotyped participants for use in PAINSTORM and beyond. The neuroimaging component will be one of the biggest to date in this patient population.

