#### 8.5. Statistical analysis of clinical data

For the primary analysis, participants will be classified as having a neuropathic or nonneuropathic component, based on their phenotype. Neuropathic phenotypes will be defined as a change of at least 2 on the sensory subscale of the EORTC-CIPN20 questionnaire and/ or dose reduction/ cessation of chemotherapy at any time during the chemotherapy. The primary analysis will be performed on the basis of these two groups. This definition may be modified as PAINSTORM Work package 2 evolves, which focuses on improving assessment to better reflect the experience of people living with NeuP(see 8.7). All continuous variables will be summarised using the following descriptive statistics: n (non-missing sample size), number of missing records, mean, standard deviation, median, maximum and minimum.

The frequency and percentages (based on the non-missing sample size) of observed levels will be reported for all categorical measures.

All summary tables will be structured with a column for NeuP group and an additional column for the total population relevant to that table/treatment, including any missing observations.

The primary analysis will examine the factors which predict the classification into the two groups and aim to establish a prediction model.

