## 14. APPENDICIES

# 14.1. Appendix 1 – Schedule of Procedures

	V1 a	V2 a	V3 a	V4 b	V5 b	V6 b	V7 b
					Follow up p	oost chemo	
	Screen & Baseline	Mid Chemo	End of Chemo	3 months	6 months	9 months	12 months
	In cli	inic/ face to	face		Postal/onlin	e/telephone	;
Informed Consent	Х						
ECOG Performance Status Scale	Х	Х	Х				
Disease progression and alterations in oncological treatment plan	х	х	х	х	х	х	х
Eligibility	Х						
Medical History	Х						
Concomitant medications	Х	Х	Х	Х	Х	Х	Х
Lifestyle (inc smoking, alcohol, ilicit drugs)	Х						
Height and weight	Х						
ActivPAL ™ physical activity monitor d	Х	Χ	Х				
Demographics	Х						
NCI CTCAE/AE	Х	Χ	Х				
QST	Х	Х	Х				
Grooved pegboard test	Х	Χ	Х				
MRI scanning	Χ		Χ				
Research Bloods	Х	Χ	Х				
EORTC CIPN 20 ce	Х	Х	Х	Х	Х	Х	Χ
List of body sites/body map ce	Х	Х	Х	Х	Χ	Х	Х
TNSc °	Х	Х	Х				
Chronic Pain Grade ce	Х	Х	Х	Х	Х	Х	Х
BPI ce	Х	Х	Х	Х	Х	Х	Х

DN4 questions e	Х	Х	Х	Х	Х	Х	Х
NeuP Symptom Inventory e	Χ	Х	Х	Х	Х	Х	Χ
	V1 a	V2 a	V3 a	V4 b	V5 b	V6 b	V7 b
EQ-5D-5L21	Χ	Х	Х	Х	Х	Х	Χ
MDASI e	Χ	Х	Х	Х	Х	Χ	Χ
PROMIS	Χ	Х	Х	Х	Χ	Χ	Χ
Pain Catastrophizing Scale	Χ	Х	Х	Х	Х	Χ	Χ
IDS-SR	Χ	Х	Χ	Χ	Χ	Χ	Χ
SOM-7	Χ	Х	X	Χ	Χ	Χ	Χ
TIPI	Χ	Х	Х	Х	Х	Χ	Χ
Saltin-Grimby Physical Activity Level Scale	Χ	X	X	X	X	Х	X

Any of the visits may be carried out over more than one day if participants wish.

<sup>a Visits 1,2 and 3 will not be on the same timescale for all patients as the visits are tailored to the patient's individual chemotherapy schedule.

<sup>b Visits 4-7 will aim to be completed within 1 month either side of scheduled clinical appointments and according to patient preference. There will be no visit windows and it will not be considered a breach of protocol if visits are missed.

<sup>c Participants will fill in pain questionnaires only if they have pain.

<sup>d If participant has opted for an ActivPalTM, they will wear that for the week prior to the cycles of chemotherapy where a face-to-face assessment is planned.

<sup>e Completed remotely (paper/ online/ telephone) prior to each cycle of chemotherapy if no face-to face visit is planned.

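### Pain scales are completed only by people in pain, but 8.5 and 8.6 make no allowance for this, and footnote c extends the rule to the EORTC-CIPN20, which defines the primary groups

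*Protocol*

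**What the plan says.** The completion rule appears twice. Protocol 3.5, in the text on timepoints, says "Pain measures are only completed if pain is present". Footnote c to the schedule in Appendix 1 (14.1) says "Participants will fill in pain questionnaires only if they have pain".

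In the schedule, footnote c is attached to EORTC-CIPN20, the body sites/body map item, Chronic Pain Grade and BPI, and apparently to TNSc (that mark is not clearly legible in the text available). DN4 and the NeuP Symptom Inventory do not carry it. They carry only footnote e, on remote completion before each cycle.

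The 3.5 table lists Chronic Pain Grade and the BPI rating under Primary, as pain severity.

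Section 8.5 summarises continuous variables by the non-missing n, the number of missing records and the usual statistics. For categorical measures: "The frequency and percentages (based on the non-missing sample size) of observed levels will be reported for all categorical measures". It defines the neuropathic group by a change of at least 2 on the CIPN20 sensory subscale and/or a reduction or cessation of chemotherapy.

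Section 8.6 says "The extent of missing data will be examined and the reason for missingness ascertained", and then "Multiple imputation (MI) may be used to impute missing values if necessary and where assumptions for missing at random data are met".

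For visits 4 to 7, Appendix 1 adds: "There will be no visit windows and it will not be considered a breach of protocol if visits are missed".

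**The concern.** Under the completion rule, a blank pain form will often mean that there was no pain. That is information about the participant, not a gap in the data. Sections 8.5 and 8.6 do not separate such a blank from a form that was never returned. A pain-severity table built to 8.5 would therefore cover people in pain only, while sitting in a plan whose population is the whole cohort.

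The second part concerns the primary classification. CIPN20 measures neuropathy, and the objective in 3.3 covers painful and non-painful CIPN. If pain-free participants skip it because footnote c says so, the people with painless neuropathy lack the measure meant to identify them.

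**Working it through.** The protocol states no figure to reproduce. Section 8.1 justifies the 200 participants in words only ("The sample size of n=200 will provide a robust, high- quality dataset of deeply phenotyped participants for use in PAINSTORM and beyond"), and no pain prevalence, mean score or SD is given. The check sets the sections side by side and then illustrates the size on stated assumptions.

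**Step 1: the summaries.** Sections 3.5 and footnote c leave Chronic Pain Grade and BPI blank when there is no pain. Section 8.5 takes means on the non-missing n and percentages on the non-missing denominator, for all variables and without exception. Together these give severity among people in pain, with pain-free people appearing only in the count of missing records.

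**Step 2: size.** Let N = 200 (8.1), p = assumed share with pain at a visit, and m = 5 = assumed mean 0-10 score among those with pain. Pain-free people have a true score of 0.

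- Blank by design = N × (1 − p)
- Mean on the non-missing sample = m
- Mean over the cohort = m × p

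| p (assumed) | Non-missing n | Blank by design | Mean under 8.5 | Cohort mean |
|---|---|---|---|---|
| 20% | 40 | 160 | 5 | 1.0 |
| 33% | 66 | 134 | 5 | 1.65 |
| 50% | 100 | 100 | 5 | 2.5 |

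Percentages scale the same way: a percentage among people in pain must be multiplied by p to become a percentage of the cohort.

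**Step 3: imputation.** If the skips were imputed from the observed forms, the result would sit near 5 as well. A simulation (1,000 cohorts of 200; scores about 5 with SD 2 in those with pain, rounded and kept within 1-10; five normal imputations each) gave means of 5.01 to 5.02 for both the non-missing summary and the imputed data. Scoring pain-free people as 0 gave 1.0, 1.65 and 2.51 at 20%, 33% and 50% with pain.

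The missing-at-random condition in 8.6 protects only partly. If pain status is not recorded, blankness depends on the unseen pain value and the condition fails. If it is recorded, the condition can seem met, but no pain-free person has an observed score, so a model can borrow only from people in pain.

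**Step 4: footnote c and the primary groups.** Section 8.5 needs a CIPN20 change, hence a baseline value and a later one. Under a literal reading of footnote c:

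- pain-free at baseline: no baseline CIPN20, so no change can be computed even if pain comes later;
- pain-free during chemotherapy: no later CIPN20, so painless neuropathy can enter the neuropathic group only through a treatment change.

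Section 7.5 makes the literal reading plausible for site staff, because it files CIPN20 under the characterisation of pain. The same section files TNSc under clinical examination, where a rule about participants filling in pain forms does not fit. DN4 and the NeuP Symptom Inventory, listed in 3.5 under type and quality of pain, fall under the general rule in 3.5 but lack the footnote. The marks and the rule need to be reconciled.

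**The case against.** The strongest reply is that scoring a skipped instrument is a derivation rule for the SAP, which 8.3 promises before database lock and which is not shown. That holds for the scoring rule alone. It does not hold for what is collected: a SAP cannot supply a CIPN20 that footnote c told a participant to omit, or a pain status that nobody asked for.

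Three stronger readings are tempting, and the protocol does not support them.

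- **That pain-free people will be given pain scores.** Section 8.6 makes imputation optional, conditional on missing at random, and preceded by finding the reason for missingness. The text leaves the possibility open but does not plan it.
- **That pain-free people disappear from the results.** Section 8.5 reports the number of missing records, and its tables include missing observations. A reader would see a small n. Severity among people in pain is also a legitimate quantity, and it suits the secondary objective of characterising NeuP. The fault is that it is not labelled as such and that no cohort-level figure is specified beside it.
- **That factors protecting against pain cannot be seen.** The primary groups rest on CIPN20 and treatment change, not on BPI or Chronic Pain Grade, so this does not follow for the primary analysis.

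It is also fair that skips can be partly recognised. EQ-5D-5L, PROMIS and IDS-SR are due at all seven visits without footnote c, and MDASI is due then and before each remote cycle. A returned set with a blank BPI suggests a skip; a wholly absent set suggests non-return. This is inference and fails for partly completed sets, which 7.5 expects by letting participants complete as many assessments as they feel able to. The web questionnaire's items are not shown, so it may contain a pain question; the protocol lists none.

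**Conclusion.** The point holds in two parts. First, the collection rule in 3.5 and footnote c is not carried into 8.5 and 8.6. As written, the Primary-listed pain scales describe only people in pain, pain-free people are counted as missing, and imputing those skips is not ruled out. Second, footnote c is attached to CIPN20 and apparently TNSc but not to DN4 or the NeuP Symptom Inventory. Taken literally, this removes the CIPN20 change for pain-free participants, against an objective that includes non-painful CIPN. The second part matters more, because it reaches the primary classification and lost data cannot be rebuilt. It depends on footnote c being applied as printed; if sites give CIPN20 to everyone, only the document needs correcting.

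The size of the first part cannot be taken from the protocol. The contrast of 5 with 1.0-2.5 rests wholly on an assumed 20-50% with pain and an assumed mean of 5 among them.

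**What to change.** 1. **Appendix 1:** remove footnote c from EORTC-CIPN20 and TNSc so that all participants complete them. Apply it consistently to the pain instruments, including DN4 and the NeuP Symptom Inventory, in line with 3.5.
2. **Collection:** record presence or absence of pain for everyone at each visit and on each remote cycle form.
3. **Section 8.5:** for cohort-level summaries, score a no-pain skip as zero, Grade 0 or negative, as the instrument requires, and keep those people in the denominator. Where severity among people in pain is reported, label it so.
4. **Section 8.6:** limit multiple imputation to forms or pain-status items truly not returned, and state that skips for absence of pain are not imputed.

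The cost is one extra yes/no item, completion of CIPN20 and TNSc by everyone where footnote c has been followed literally, and a few lines of text. No visits or participants are added. Items 1 and 2 are worth most while data are still being collected.

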#### 8.7. Other statistical considerations.

One of the PAINSTORM work packages aims to establish patient centred outcomes and disease classification which may be more important to the patient groups. As that work package is not completed, those outcomes are not currently available. It is expected that the work package will create results prior to the analysis of this study, and an iterative approach will be used to ensure that outcome measures are meaningful to people living with the condition. Any important findings from the work package will be included in the SAP and run as an exploratory analysis.

#### 9. DATA MANAGEMENT

#### 9.1. Data collection tools and source document identification

Imaging data will be pseudo-anonymised with a code, extracted from the scanner then stored on the University of Dundee Life Sciences Compute Cluster for backup and analyses. Statistical analyses will be done using standard neuroimaging computational methods: e.g. Matlab, Statistical Parametric Maps, FSL, Freesurfer, R. The data will be stored and backed up in the Life Sciences Compute Cluster, University of Dundee and analyses done there, the other will go to HIC for the ALLEVIATE data hub or equivalent.

Questionnaires will be returned to HIC using the pseudo-anonymised study code for identification, where data will be entered on the study database, managed by HIC.

Medical records/ study questionnaires will be used as source data. All study data relevant to a participant's general medical history will be recorded in the medical records. Essential information regarding study participation will also be recorded in the medical records.

Details of datasets transfer, storage and analysis will be documented in the Data Management Plan.

#### 9.2. Data handling and record keeping

Data will be stored in the Health Informatics Centre (HIC), and the Life Sciences Compute Cluster, University of Dundee. HIC has access-controlled data server rooms contain 2 separate networks which hold all identifiable NHS data or University research data; this facility is only accessible to HIC staff who have provided a Disclosure Scotland security certification and have completed a confidentiality agreement. Industry standard login access controls are in place across all HIC infrastructure, in line with University of Dundee best practice. HIC facilities and processes are audited at least once annually by external auditors as part of the HIC ISO27001 certification.

Data management will be undertaken in close collaboration with HIC Services who will develop the Data Management System (DMS). An anonymised copy of neuroimaging data, pain and psychological ratings data, will also be stored in the secure Life Sciences Compute Cluster where the computationally intensive neuroimaging analyses will be carried out. The DMS will be based on the protocol for the study. All services provided by HIC are delivered within a secure environment to ensure data are managed safely and in compliance with Data Protection legislation, and all HIC processes are governed by approved SOPs. The PAINSTORM data will be housed in Alleviate (Advanced Pain Discovery Platform Data Hub), within HIC as a resource for the wider pain research community, subject to appropriate data governance measures. The DMS is managed in line with all applicable principles of medical confidentiality and UK law on data protection. The Data Controller will be the University of Dundee and the Data Custodian will be the PI.

Development and validation of the study DMS, quality control and extraction of data will be done according to local SOPs. Extracts for analysis will be managed by the PI.

#### 9.3. Access to Data

Direct access will be granted to authorised representatives from the Sponsor, host institution and the regulatory authorities to permit study-related, audits and inspections - in line with participant consent.

#### 9.4. Archiving

Archiving will be authorised by the Sponsor following submission of the end of study report. All essential documents will be archived for a minimum of 5 years after end of study, destruction of essential documents will require authorisation from the Sponsor. Medical notes will be maintained in compliance with local NHS Policy on Retention of Medical Case notes.

## 10. AUDIT & INSPECTION

The CI, PI and all institutions involved in the study will permit study-related monitoring, audits, and REC review. In the event of an audit, the CI will allow the Sponsor, representatives of the Sponsor or regulatory authorities direct access to all study records and source documentation.

#### 11. ETHICAL AND REGULATORY CONSIDERATIONS

#### 11.1. Research Ethics Committee (REC) review & reports

Before the start of the study, approval will be sought from a REC for the study protocol, ICFs and other relevant documents. Substantial amendments that require review by REC will not be implemented until the REC grants a favourable opinion for the study.

All correspondence with the REC will be retained in the Study Master File. A copy of all REC reports will be submitted to the Sponsor.

An annual progress report will be submitted to the REC within 30 days of the anniversary date on which the favourable opinion was given, and annually until the study is declared ended. It is the Chief Investigator's responsibility to produce the annual reports as required.

The CI will notify the REC of the end of the study. If the study is ended prematurely, the CI will notify the REC, including the reasons for the premature termination

Within 1 year after the end of the study, the CI will submit a final report with the results, including any publications/abstracts, to the REC

#### 11.2. Peer review

Extensively reviewed by the funders (UK Research and Innovation/ Versus Arthritis/ Eli Lilly, coordinated by Medical Research Council with external peer review) as part of the award process.

#### 11.3. Public and Patient Involvement

The PAINSTORM proposal was developed by a team of patients, clinicians and researchers, inspired by research and conversations with people living with NeuP. Patient partners have actively shaped content to ensure unmet needs have been addressed. Discussions with people living with NeuP were held to uncover relevant research priorities for PAINSTORM, centred on individuals experience of pain and the best way to assess pain.

Three people have volunteered to be patient partners for PAINSTORM Dundee on the main research team, all of whom have also been involved throughout the pre-funding stage. The protocol has been reviewed by some of the patient partners. Patient partners are invited to attend REC meetings so that they can describe what is being done with patients in patient/public facing materials (eg information leaflets). All information material, such as PISs and lay summaries, have been written in plain English and reviewed by the patient partners to ensure people can find out what they want to know in an understandable way. The patient partners are integral members of the SMG and attend meetings to give their input into how the study is being carried out. Patient partners will be involved in analysis and interpretation of findings to ensure that emerging knowledge makes sense to those with lived experience.

We are working with relevant third sector organisations (Maggie's Centre, Tayside Cancer Support, CanDu) to reduce barriers to participation and provide additional support when required.

## 11.4. Regulatory Compliance

The study will not commence until favourable REC opinion is obtained. Before the site can enrol participants into the study, the CI/PI or designee will ensure that appropriate approvals (NHS R&D) from the participating organisation is in place.

For any amendment to the study, the CI or designee, in agreement with the sponsor, will submit information to the appropriate body in order for them to issue approval for the amendment. The CI or designee will work with the site (R&D department at NHS site as well as the study delivery team) so they can put the necessary arrangements in place to implement the amendment to confirm their support for the study as amended.

#### 11.5. Protocol compliance

Prospective, planned deviations or waivers to the protocol are not allowed and must not be used e.g. it is not acceptable to enrol a participant if they do not meet the eligibility criteria or restrictions specified in the study protocol. Accidental protocol breaches can happen at any time. They must be adequately documented on the relevant forms and reported to the CI and Sponsor immediately.

Breaches from the protocol which are found to frequently recur are not acceptable, will require immediate action and could potentially be classified as a serious breach.

In the event that there is a breach of the protocol, the nature of and reasons for the breach will be recorded in the TMF and documented in the study Breach Log and reported to Sponsor via the breach reporting process.

